### Summary:

The rehabilitation of the upper limb after a stroke is a challenge due to its complexity and the important cerebral representation of it, particularly of the hand. Repetitive transcranial magnetic stimulation (rTMS) is a tool that can broaden the effect of rehabilitation and thus appears to be observed in different studies performed in patients in chronic phase. However, we have little data on its usefulness before 6 months after the stroke. The variability in the presentation and the fact that it is a phase where the motor deficit of the upper limb coexists with other deficits and medical problems partly explain the lack of specific studies.

We present here a preliminary study on the efficacy of rTMS associated with the rehabilitation program of the paretic upper extremity due to a stroke in comparison with sham rTMS. Patients (with moderate to mild involvement) will be randomly distributed in the two study groups and will be evaluated both clinically and neurophysiologically before and after the sessions to try to show if there is a positive effect safely.

# Introduction:

Stroke is the leading cause of acquired disability in the world (Donnan et al, 2008). Although in recent years there has been a real revolution in treatments in the acute phase of ischemic stroke, up to 60% of patients who have suffered it show some alteration of manual dexterity at 6 months (Lai et al. 2002). Rehabilitation plays a positive role in improving the functionality of patients, but it is very unlikely that a patient who does not recover manual functionality can perform, for example, the same work that was previously performed (Kwakkel et al, 2002).

Different rehabilitation techniques have been added in recent years to the catalog of what has been classically called "conventional treatment" in order to maximize its effectiveness (Claflin et al, 2015) and one of them is the use of non-invasive stimulation. Non-invasive stimulation includes transcranial direct current stimulation (tDCS) and repetitive transcranial magnetic stimulation (rTMS). The latter manages to induce an electric current that leads to neuronal depolarization through rapid changes in the magnetic field induced by a coil. The objective is to modulate the cortical excitability and induce functional plasticity that allows a better motor learning when the specific motor tasks of the rehabilitation treatment are performed (Reis et al., 2008).

Generally, non-invasive stimulation has been based on two principles: of increasing the excitability of the affected hemisphere (which is translated at the level of rTMS in performing a stimulation at frequencies greater than 5 Hz) or of reducing that of the healthy hemisphere (with stimulation frequencies equal to or less than 1 Hz) to minimize intracortical inhibition that may exert on the affected hemisphere (Takeuchi 2012). Besides the question of the type of stimulation, another determining factor is its dosage: There is a presumption that more intensity and longer duration is usually associated with a greater effect, although this in turn could increase the risk of side effects with seizures, headache or nuchal pain, as well as greater operational difficulties. In this sense, consensus has been established through different guidelines for applying the techniques in a safe manner (Wassermann et al, 1998).

The majority of studies that have evaluated the use of rTMS for the improvement of the upper limb have been performed in chronic patients with inhibitory stimulation contralateral to the lesion. We can say that in this case, based on the published studies, there is a level of evidence B in relation to this assumption. (Lefaucheur et al 2014, Emara et al 2010). However, some studies have also been conducted with fewer patients in acute and subacute phases with different results (Seniow et al 2012, Sasaki 2013, Zheng 2015) and even a few works with high frequencies in the injured hemisphere (Khedr 210 et al. al, Emara et al 2010). Another issue addressed by these studies is to know which is the best of the therapies to be associated with the stimulation and the degree of synergy of both activities (Avenanti et al 2012, Seniow et al 2012).

In relation to the location of the lesions, some studies suggest that the benefit of the effect would be greater in the case of subcortical lesions than in those cases of cortical involvement (Ameli et al 2009, Emara et al 2009); less information we find about what are the neurophysiological characteristics that indicate a greater response.

In summary, rTMS is a tool that can be useful to improve the response of rehabilitation treatment of upper limb paresis after a stroke, although this seems more evident in the case of chronic patients. We do not know, however, which are the most correct parameters and the best rehabilitation to be applied jointly, as well as knowing the type of patients that will have a greater benefit. In our particular case we want to obtain data that indicate the efficacy of low-frequency rTMS contralateral to the lesion associated with our rehabilitation treatment protocol in acute / subacute patients (less than 6 months of evolution).

#### Outcomes:

- Primary outcome:
- To evaluate the efficacy of low-frequency rTMS contralateral to the lesion in patients with stroke in the subacute phase (<6 months), associated with rehabilitation treatment in the improvement of functionality of the paretic upper limb.

Secondary outcome:

- To analyze the presence of neurophysiological differences between patients who have received rTMS associated with rehabilitation of the upper limb and patients who have undergone such treatment after sham stimulation in the subacute phase.
- Establish the clinical and neurophysiological elements that may indicate that patients respond better to rTMS plus rehabilitation of the upper extremity in subacute phase
- Evaluate the safety of rTMS associated with rehabilitation in subacute patients with stroke.

# **Hypothesis:**

Low-frequency rTMS contralateral to the injury in patients with stroke in the subacute phase (<6 months) improves the rehabilitation performance of the upper limb in a safe manner

# **Material and Methods:**

#### 1) DESIGN

The study presents a randomized design (rTMS vs simulated stimulation) in patients with a single stroke of less than 6 months of evolution and unialteral involvement, who have a brachial paresis with scores on the Fugl Meyer scale (FM)  $\geq$  22 in the upper limb. The different clinical evaluations (previous and result of the intervention) will be carried out blindly with respect to real or simulated rTMS realization. To do this, patients will be selected who come to our center on an admission or outpatient basis.

The intervention phase will last 3 weeks (daily sessions from Monday to Friday), completing a final of 15 sessions. In each session EMTr would be performed first and immediately the rehabilitation treatment of the upper limb based on the protocol of our center (1 specific hour, within the integral program). Evaluations will be made before the intervention, at the end of the intervention and one month later.

• Patients: Patients with a stroke (ischemic-hemorrhagic) that conditions a unilateral limitation (brachial monoparesis or hemiparesis) and that presents a moderate or mild deficit (motor score on the FM scale  $\geq$  22 at motor level of the upper extremity) .To Participate in the study the patients must sign an informed consent and be > 18 y.o. Patients with epilepsy or those with electrical devices in their body or metallic ones in the brain, as well as patients with craniotomy without cranioplasty, will be excluded from the study. All patients whose medical conditions prevent them from complying with the rehabilitation protocol will be excluded

- rTMS: Patients will be distributed randomly in real or sham rTMS before the specific rehabilitation treatment. To do this, a Magstim Super Rapid magnetic stimulator (Magstim Company, Whitland, Wales, UK) equipped with a double cone coil was used to position it on the cranial cortex. Simulated stimulation will be performed by placing the same coil without being connected, but maintaining the characteristic noise of the stimulation (all this assembly will be kept out of the patient's visual field). The rTMS intensity is calculated over 90% of the motor threshold, evaluated by EMG of surfaces, of the first dorsal interosseous of the hand without motor involvement. From this intensity, adjustments can be made depending on the tolerance. This system has been previously carried out in different studies of ours and other groups for different pathologies, proving safe and tolerable. For rTMS 1500 pulses of 1 Hz frequency will be used at the sub-threshold intensity commented on the optimal score in M1 of the unaffected hemisphere (in relation to the first interosseous dorsal muscle). The simulated rTMS will be applied during the same time. The patient will be in a sitting position while the technique is performed.
- Rehabilitation treatment of the upper limb: The rehabilitation treatment protocolized in our center will be followed within the comprehensive stroke treatment program. According to this protocol, there would be differences between a moderate patient (FM upper extremity motor between 22 and 45) and mild (FM upper limb motor greater than 45).
- Moderate: Active mobility work, proprioceptive treatment, exercises with reality virtual and biofeedback and use of robotic systems with multiple repetitions.
- Mild: Work of active mobility, proprioceptive treatment, exercises with reality virtual and biofeedback, as well as restrictive therapy.

In any case, to compensate for the potential variability of rehabilitative work, the therapist will be blind to the condition of real or simulated stimulation of the patient.

- Clinical evaluation: A specific clinical evaluation will be carried out before, at the end of the treatment and a month after the same. In this evaluation the FM, Block Test, 9- HPT and ARA Test scale will be evaluated. In turn, spasticity in the muscle groups of the upper extremity will be evaluated using the modified Ashworth scale (Bohanson & Simth 1987) and an analogue numerical scale (from 1 to 10) according to the patient's assessment. In turn, demographic data (sex, age) and stroke characteristics (classification, location, NIHSS) will be registered in the first visit.
- Neurophysiological evaluation: The neurophysiological evaluation will be carried out before the first session and after the end of the intervention phase. The evaluation will be performed with the patient seated, using Ag-AgCl bipolar surface electrodes and a routine electrodiagnostic device using bipolar Ag-AgCl surface electrodes and a CED Spike electrodiagnostic device (CED Micro 1401 analog-to digital system). The motor evoked potentials of the first dorsal interosseous of hand hands will be evaluated, calculating the motor threshold, the recruitment curve and the paired impulse curve. For this, stimuli will be performed by Magstim Super Rapid EMT (Magstim Company, Whitland, Wales, UK) equipped with a focal coil to position it on the cranial cortex. The minimum threshold will be considered to be the motor threshold for at least 5 evoked potentials of at least 50 μV in 10 stimuli.
- Statistical analysis: Changes in the clinical scales (FM and ARA Test) between the two groups will be compared by means of nonparametric tests (Mann-Whitney T test) or, if the normality (Kolmogorov-Smirnov) is not rejected, the TTest test. In addition, the response variables (in these three tests) will be related to various demographic, neurophysiological variables and the characteristics of their disease), using the test to obtain a confidence of 95% and a power of 80%, it is estimated that the sample size it must be at least 10 subjects in each group (the objective of the study will be a minimum of 24 subjects to improve the statistical weight).

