#### 2) LIMITATIONS

The present study shows a series of limitations, most of them intrinsic to the difficulty of the object of the same and to the characteristics of the rehabilitation treatment. The aim of the study is to find indications of the efficacy of rTMS in the subacute phase for the improvement of the functionality of the upper extremity in stroke, which allows us to consider studies of a larger sample size and a more homogeneous sample.

- Strokes show great variability in etiology, location and response to rehabilitation treatment. We will try to perform a subanalysis of all these factors, although the sample size will not allow us to reach definitive conclusions.
- The radiological variables will be analyzed in a qualitative way, given the diverse origins with different characteristics of the patient's image tests
- The rehabilitative treatment, although it is protocolized, presents a variability marked by the necessary individualization (since we maintain the usual treatment of our center). This limitation is tried to compensate with the condition of blind for the condition of stimulation of the patient on the part of the therapist.
- The rhythm of patient recruitment can be variable given the characteristics of the patients who enter our center according to the stroke plan (patients with an important affectation, many of them severe and very severe in relation to the upper limb, and who in principle, it is unlikely that they can benefit from rTMS).

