### - 1st month:

Start-up of the study, assessing in an initial patient the mechanics of evaluation and intervention measures in a coordinated manner. Randomization plan for patients. Before start the study will register the same in the trials.gov page

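### No allocation method is specified, and Fugl-Meyer band, which sets part of the rehabilitation, is neither balanced by design nor adjusted for in the main comparison

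*Combined protocol and SAP*

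**What the plan says.** Allocation is covered in one sentence of Material and Methods, 1) DESIGN, under rTMS: "Patients will be distributed randomly in real or sham rTMS before the specific rehabilitation treatment". The work plan lists "Randomization plan for patients" as a task for the first month and says nothing about its content. The ratio, restriction, stratification and concealment are not given anywhere.

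Under rehabilitation treatment, the same section says "there would be differences between a moderate patient" (FM 22 to 45) and a mild one (FM above 45). Both bands receive active mobility, proprioceptive work, virtual reality and biofeedback. The moderate band adds robotic systems and the mild band adds restrictive therapy.

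To offset variability in rehabilitation, the plan blinds the therapist to stimulation condition. The limitations section repeats this: "This limitation is tried to compensate with the condition of blind".

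The statistical analysis paragraph compares FM and ARA changes between groups by Mann-Whitney or t test, with no term for FM band. On size it says "it is estimated that the sample size it must be at least 10 subjects in each group", and that "the objective of the study will be a minimum of 24 subjects to improve the statistical weight".

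**The concern.** FM band is a baseline measure of severity and also selects part of the co-intervention. If one arm receives more moderate patients by chance, it also receives more robotics and less restrictive therapy, and its room and potential to improve may differ. An unadjusted comparison of change carries that difference into the estimated rTMS effect, where it could add to a real effect, hide one or resemble one.

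The safeguard offered addresses something else. A blinded therapist cannot favour an arm. Blinding has no influence on how many patients of each band were allocated to each arm.

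The study is meant to indicate whether larger trials are worthwhile, so a misleading estimate from a single sample of about 24 matters. A smaller question is whether the stated minimum per group is secured.

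**Working it through.** **Inputs from the protocol.** Total N = 24 (a minimum); at least 10 per group; 95% confidence and 80% power; FM bands 22 to 45 and above 45.

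**Assumptions, because the protocol is silent.** Ratio 1:1; two-sided test; number of moderate patients K between 8 and 16 of 24.

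**1. The plan's own figure.** Ten per group cannot be reproduced, since no effect size, SD or sidedness is given. Solving backwards with the normal formula, d = √(2/10) × (1.960 + 0.842) = 1.25. With the t distribution, d = 1.32.

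**2. FM-band imbalance at exactly 12:12.** Let A be the number of moderate patients in one arm. Without stratification A is hypergeometric (24 patients, K moderate, 12 drawn), and the arms differ by |2A − K| moderate patients.

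For K = 12, a difference of 4 or more means A ≤ 4 or A ≥ 8:

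2 × (1 + 144 + 4,356 + 48,400 + 245,025) / 2,704,156 = 595,852 / 2,704,156 = 22.0%.

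For odd K the difference is always odd, so 4 or more means 5 or more. For K = 9, A ≤ 2 or A ≥ 7:

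2 × (455 + 12,285 + 108,108) / 2,704,156 = 241,696 / 2,704,156 = 8.9%.

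| K moderate of 24 | P(difference ≥ 4) |
|---|---|
| 8 or 16 | 19.3% |
| 9 or 15 | 8.9% |
| 10 or 14 | 21.4% |
| 11 or 13 | 9.9% |
| 12 | 22.0% |

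The range over K = 8 to 16 is 9% to 22%.

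**3. Size of the resulting shift (illustration).** In an 8:4 split the arms differ in share moderate by 8/12 − 4/12 = 1/3. If mean change differed between bands by 0.5 to 1.0 within-band SD (an assumption; the protocol gives no value), the unadjusted difference would move by 0.17 to 0.33 SD in that sample.

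**4. Arm size if allocation were simple 1:1.** P(an arm has 9 or fewer) = 2 × P(Bin(24, 0.5) ≤ 9) = 2 × 2,579,130 / 16,777,216 = 30.7%. The same calculation gives 16.9% at N = 26, 8.7% at 28 and 4.3% at 30.

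**5. Power at unequal splits of 24.** Noncentral t, two-sided 5%, d = 1.32 from step 1:

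| Split | Power |
|---|---|
| 12:12 | 87.3% |
| 15:9 | 85.1% |
| 16:8 | 83.2% |
| 17:7 | 80.5% |
| 18:6 | 76.6% |

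On this t-test calculation power drops below 80% only at 18:6 or worse, which has probability 2.3% under simple allocation.

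**6. Check of the remedy.** With permuted blocks no larger than 4 within each of two bands, only the last block in a band can be incomplete, so the arms differ by at most 2 in each band and 4 overall. At N = 24 the smaller arm has at least (24 − 4)/2 = 10. With blocks of 6 the largest overall difference is 6, so an arm of 9 remains possible.

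**The case against.** The strongest reply is that the documents never call the randomisation simple or unstratified. A randomisation plan is scheduled before the patients of months 2 to 15, and it may contain blocks and strata. This stands: the finding is that the method is unreported, and the figures in steps 2 and 4 describe what follows if no stratification, or no restriction, is used. It does not remove the point, because the analysis as written still has no term for FM band.

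A reader might infer that the trial has a 31% chance of being underpowered. The documents do not support that. The figure requires simple allocation and exactly 24 patients, whereas 24 is a minimum. Also, 15:9 is not 9:9, and it keeps about 85% power at the effect that 10 per group implies.

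A reader might also infer that arm is confounded with rehabilitation type. It is not. FM band sets the programme in the same way in both arms, the programmes share most components, and randomisation leaves the comparison unbiased on average. What remains is added variance and conditional bias in the sample actually obtained.

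Finally, the plan relates response to disease characteristics and promises a subanalysis of stroke variability. By its own account the sample is too small for that to be conclusive, and it does not alter the group comparison. The blinding statement is fair as protection against different handling by arm; it falls short only as an answer to imbalance in who receives which programme.

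**Conclusion.** The point holds in limited form. The allocation method is not reported, and nothing described in the design or the main comparison balances or adjusts for the variable that sets part of the rehabilitation. Therapist blinding does not fill that gap. If allocation is not stratified, the chance of a difference of 4 or more moderate patients at 12:12 is 9% to 22%, given 8 to 16 moderate patients among 24. The share of moderate patients is an assumption, and the harm depends on how far the bands differ in recovery, which the documents do not state.

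Group size is secondary: 31% for an arm below 10 under simple 1:1 allocation at 24, 8.7% at 28, with little loss of power. This is an inexpensive improvement that should be made, not a flaw that invalidates the trial.

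**What to change.** - In the month 1 randomisation plan, specify concealed 1:1 allocation in permuted blocks of randomly varying size 2 and 4, stratified by FM band (22 to 45, above 45). This secures at least 10 per arm at allocation with N = 24. It does not protect against dropout.
- Adjust the main comparison for FM band or baseline FM, for example by ANCOVA, or by a stratified Wilcoxon test if the data are not normal.
- Reword the two blinding statements to say that therapist blinding limits differential treatment by arm only, and report rehabilitation modality and minutes by arm.

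**Cost.** No extra patients and no new assessment, since FM is already measured before the intervention. Recording modality and minutes adds a little work. Small blocks make the next allocation slightly more predictable; concealment and varying block size keep that risk low.

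### Time since stroke is neither listed for recording nor used in the group comparison, so a chance imbalance in it could distort this small trial's result unseen and uncorrected

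*Combined protocol and SAP*

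**What the plan says.** All references are to the combined protocol and SAP.

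- **Eligibility** (1) DESIGN): "patients with a single stroke of less than 6 months of evolution". No minimum time is given. The Introduction describes the target population as acute and subacute together.
- **Data at the first visit** (1) DESIGN, Clinical evaluation): besides the patient's sex and age, the plan states that "stroke characteristics (classification, location, NIHSS) will be registered in the first visit". Neither the date of stroke nor time since stroke is listed.
- **Group comparison** (1) DESIGN, Statistical analysis): the method is given as "Changes in the clinical scales (FM and ARA Test) between the two groups will be compared by means of nonparametric tests (Mann-Whitney T test", with a t test instead if normality is not rejected. No covariate is named.
- **Exploratory analysis** (same paragraph): the response variables "will be related to various demographic, neurophysiological variables and the characteristics of their disease". This is a separate analysis from the comparison of arms, and it does not name time since stroke.
- **Allocation** (1) DESIGN, rTMS; work plan, first month): random. No stratification is described.
- **Limitations** (2) LIMITATIONS): "Strokes show great variability in etiology, location and response to rehabilitation treatment". Time since stroke is not among the factors named for subanalysis.

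**The concern.** Time since stroke defines this trial's population, and the Introduction separates evidence in chronic patients from evidence in earlier phases. If improvement depends on how recently the stroke occurred, an arm that happens to hold more recent strokes will improve more whether or not rTMS works. With about 24 patients, a gap of several weeks between arms is plausible.

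The documents protect against this at no stage. Allocation is not described as stratified, the variable is not on the recording list, and the comparison does not adjust for it. A reader of the results could not tell from the listed data whether the arms were comparable on it. The study's stated aim is to find indications of efficacy that would justify a larger trial, so one distorted comparison could sway that decision in either direction.

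**Working it through.** **The plan's own figure.** The plan states at least 10 per group for 95% confidence and 80% power, with a target of at least 24 in total. It gives no effect size or SD, so the 10 cannot be reproduced. Solving backwards with a two-sided t test, 10 per group at 80% power implies a standardised effect of about 1.32.

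**Inputs.** From the documents: entry under 6 months, a target of 24 patients, and an unadjusted comparison of change. Assumed, because the documents do not give them: 1:1 allocation (12 per arm), uniform entry over a window of W weeks, the share R² of the variance in change explained by time since stroke, and a 1.0 SD effect for power.

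**Step 1: how large a gap can arise by chance.** SD of time since stroke = W/√12. SE of the difference in arm means = SD × √(2/12).

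| Entry window W | SD (weeks) | SE of difference (weeks) | P(gap > 4 weeks) |
|---|---|---|---|
| 26 weeks | 7.51 | 3.06 | 19% |
| 20 weeks | 5.77 | 2.36 | 9% |
| 13 weeks | 3.75 | 1.53 | 1% |

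For W = 26, the 95% range of the difference is 1.96 × 3.06 = ±6.0 weeks.

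**Step 2: what a gap does to the unadjusted result (W = 26).** A gap of 4 weeks shifts the group difference by √R² × 4/7.51 outcome SDs. Type I error was simulated with no treatment effect (100,000 trials per row). The adjusted model contains treatment, baseline score and time since stroke.

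| R² | Shift from a 4-week gap (SD) | Unadjusted, all trials | Unadjusted, gap > 4 weeks | Adjusted, gap > 4 weeks |
|---|---|---|---|---|
| 5% | 0.12 | 5% | 6% | 5% |
| 10% | 0.17 | 5% | 7% | 5% |
| 20% | 0.24 | 5% | 10% | 5% |
| 30% | 0.29 | 5% | 12% | 5% |

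**Step 3: what adjustment does to power.** With 12 per arm and a 1.0 SD effect, unadjusted power is about 65%. The t test has 24 − 2 = 22 residual degrees of freedom. The model with two covariates has 24 − 4 = 20.

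| R² of time since stroke | Adjusted power, baseline score explains nothing | Adjusted power, baseline score explains a further 10% |
|---|---|---|
| 5% | about 63% | about 67% |
| 10% | about 65% | about 70% |
| 20% | about 70% | about 76% |
| 30% | about 75–76% | about 82% |

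At the 1.32 SD effect implied by the plan's own sample size, unadjusted power is already 87%. Adjusting for time since stroke alone gives 89% if its correlation with change is 0.3, and 94% if it is 0.5.

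**The case against.** The strongest reply is that randomisation already deals with this. That is correct on average: over all simulated trials the unadjusted test keeps its 5% level and the mean difference is about zero. A reader might infer that leaving time since stroke out makes the planned comparison biased or invalid. The documents do not support that. The distortion exists only given a realised imbalance.

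A second reply is that the stroke date must be known to check eligibility, and that a short bracketed list is not a data dictionary. This also stands in part: nobody should conclude that the date will be unavailable. But the plan does not commit to keeping it as study data, showing it by arm or using it. The generic line on disease characteristics could include it, but that line is separate from the comparison of arms.

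A third reply is that the sizes rest on assumptions. They do. No passage gives the entry distribution or says how strongly recovery depends on time since stroke, and a narrower entry window makes a large gap rare. The change to the end of treatment also spans only about 3 to 5 weeks by the work plan (three weeks of sessions, assessed the week before and the week after), which leaves limited time for differential recovery.

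Finally, this is a preliminary study that admits its limits, and adjustment does not guarantee more power. With weak covariates it loses about 2 percentage points (65% to 63%).

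**Conclusion.** The concern holds as a conditional one. Time since stroke is missing from the recorded list and from the group comparison. If the arms differ on it by chance, the plan as written would neither reveal nor correct the effect. The planned test remains valid over repeated randomisations.

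Under uniform entry over 26 weeks there is about a one-in-five chance of a gap above 4 weeks, and given that gap the type I error is about 6 to 12% instead of 5%. The first figure depends on the entry window and the second on an R² of 5 to 30%; neither is known from the documents. The effect of adjustment on power ranges from a slight loss to a clear gain. The firmer reasons for the change are that balance becomes visible and that the covariate is chosen before the data are seen. It should be made because it is cheap, not because the unadjusted analysis is wrong.

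**What to change.** 1. Add the date of stroke to the first-visit data, and tabulate days from stroke to first session by arm.
2. Replace the t test/Mann-Whitney scheme with a pre-specified linear model of change on treatment, baseline score and days from stroke, for FM and for ARA. Neither planned test takes a covariate, so this replaces the method and is more than an added phrase.
3. State the fallback: if residuals are clearly non-normal, use a rank-based ANCOVA or a permutation test of the same model.
4. Keep the unadjusted test as a sensitivity analysis.

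Eligibility, treatment and visits are unchanged. The cost is one data field whose value is needed at screening anyway, a rewritten analysis paragraph and two degrees of freedom. If neither covariate is informative, the price is the small loss of power shown above.

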# -2nd to 15th month:

Carrying out of the study, with the realization of the first clinical and neurophysiological evaluation of each patient the week before performing the rTMS and the week after the end of the stimulation. A new clinical evaluation will be carried out at 4 weeks (± 1 week)

- 14th to 18th month:

Analysis of the data and starting of their dissemination.

ERES	IN STITUT GUTTMANN HOSPITAL DE NEURODEHABILITACIÓ Institut Universitari adsorit a la UMB

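### No primary scale, visit or success rule is named: FM and ARA are compared unranked, so if either sufficed at one visit the false-positive risk would be about 8%-9.5% (assumed correlation 0.3-0.8)

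*Combined protocol and SAP*

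**What the plan says.** - **Outcomes.** The primary outcome is an aim: to evaluate low-frequency rTMS contralateral to the lesion, "associated with rehabilitation treatment in the improvement of functionality of the paretic upper limb". No scale, visit or summary measure is attached.
- **Design, Clinical evaluation.** FM, Block Test, 9-HPT and ARA are recorded. Spasticity is assessed by the modified Ashworth scale and a 1-10 numerical scale. On timing: "A specific clinical evaluation will be carried out before, at the end of the treatment and a month after the same".
- **Design (opening text) and Pla de Treball.** The schedule is repeated: "Evaluations will be made before the intervention, at the end of the intervention and one month later", and "A new clinical evaluation will be carried out at 4 weeks", with a one-week tolerance.
- **Design, Statistical analysis.** The first choice reads "Changes in the clinical scales (FM and ARA Test) between the two groups will be compared by means of nonparametric tests (Mann-Whitney T test", with a t-test if normality is not rejected. Then "the response variables (in these three tests) will be related to various demographic, neurophysiological variables", although only two scales have been named.
- **Sample size, same paragraph.** "using the test to obtain a confidence of 95% and a power of 80"%, giving at least 10 per group, with a target of at least 24 subjects. No scale, visit, effect size or SD is stated.
- **Summary.** Patients "will be evaluated both clinically and neurophysiologically before and after the sessions to try to show if there is a positive effect safely".

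**The concern.** The Hypothesis section predicts that rTMS improves upper-limb rehabilitation, but nothing says which result would confirm this. Three choices are open in this document: the scale, the visit, and whether one scale or both must differ. Nothing here prevents them from being settled once the data are known. The mention of three tests after two named scales leaves the set of response variables unclear as well.

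The open choices give different trials. Accepting either scale raises the false-positive risk above 5%. Requiring both lowers it when neither scale is affected, and costs power. The Limitations section says the result is meant to support larger studies. An apparent effect taken from whichever scale or visit looks best would be weak support for them.

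**Working it through.** **1. The plan's own figure.** It is at least 10 per group at 95% confidence and 80% power. Without an effect size or SD it cannot be reproduced, only inverted for a single two-sided comparison:

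- Normal formula: (1.960 + 0.842) × √(2/10) = 1.25 standardised units. Noncentral t: 1.32.
- With 12 per arm (24/2), noncentral t: 1.20.

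Other rules also reach 80% with 10 per group, assuming equal effects on both scales and correlation 0.3-0.8: about 1.05-1.2 if either scale suffices, and about 1.45-1.5 if both are required. The stated 80% therefore does not identify a rule.

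**2. Inputs for the error rates.** From the plan: two scales, two post-baseline visits, a 5% level (95% confidence) and a target of 24. Assumed, because the plan is silent: equal arms of 12, two-sided tests, correlation 0.3-0.8 between scales, and no true effect on either.

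**3. One visit, two scales.** With each test at 5%:

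- P(either) = 0.05 + 0.05 − P(both).
- P(either favouring rTMS) = 0.025 + 0.025 − P(both favouring rTMS).

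Bivariate normal results:

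| Correlation | Both | Either | Both, favouring rTMS | Either, favouring rTMS |
|---|---|---|---|---|
| 0.3 | 0.0049 | 0.0951 | 0.0024 | 0.0476 |
| 0.5 | 0.0093 | 0.0907 | 0.0046 | 0.0454 |
| 0.8 | 0.0219 | 0.0781 | 0.0110 | 0.0390 |

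Under independence the bound for either scale is 1 − 0.95² = 0.0975. Relative to 5%, the either-scale rule gives 7.8/5 = 1.6 to 9.5/5 = 1.9 times nominal. Simulated t-tests (12 per arm, 200,000 null trials) at correlations 0.3 and 0.8 agree: either 9.4% and 8.0%; both 0.5% and 2.1%.

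**4. Mann-Whitney, the test named first.** With 12 per arm the exact test rejects at U ≤ 37, an attained level of 4.5%. Either scale at one visit then gives about 7%-9% (3.6%-4.3% favouring rTMS).

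**5. Both required, but only one scale truly affected.** As the true effect on one scale grows, its test becomes almost certain to reject. The chance of a false result on both scales then approaches the level of the other test: 5% in either direction, 2.5% favouring rTMS.

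**6. Either scale at either visit.** With an assumed correlation of 0.5-0.9 between visits, the risk is about 11%-17% (5.5%-8.5% favouring rTMS).

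**7. Power.** With 12 per arm and a true standardised difference of 1.20 on both scales:

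- One named scale: 80%.
- Either suffices: 88%-94%.
- Both required: 67%-73%.
- At least one success under Holm: 79%-88%.
- A given scale at Holm's first step (2.5%): 70%; it needs a difference of 1.34 for 80%.

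**The case against.** The strongest reply is that this is a preliminary study. The Summary says so, and the Limitations section seeks only signs of efficacy that would support larger trials. That stands as a reason to moderate the weight. It does not supply an endpoint, and the plan also states a directional hypothesis, a primary outcome and an 80% power target.

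It can also be said that the visit is implied. The Summary refers to assessment before and after the sessions, and the Design section describes the clinical evaluations as those preceding the intervention and those giving its result. Both lean towards the end-of-intervention visit, but neither designates it. FM sets eligibility and the severity bands, yet no passage ranks it above ARA.

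The work plan puts registration before the start, and the registry record is not available to me. The choice may have been fixed there; the gap in this document remains.

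Several stronger conclusions are tempting but not supported:

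- **That error simply doubles.** This is near the upper end. At correlation 0.8 the factor is about 1.6, and it is lower with the exact Mann-Whitney test.
- **That 80% power contradicts both rules.** With no effect size stated, 80% can fit either.
- **That requiring both scales always keeps error below nominal.** The 0.5%-2% holds only if neither scale has an effect.
- **That 11%-17% is the planned error rate.** Testing both visits is a possible reading, not a stated plan.
- **That three tests means a third between-group comparison.** The phrase concerns relating responses to covariates and identifies no third scale.

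**Conclusion.** The point holds and should be fixed. The gap in the text needs no assumption: no primary scale, visit, success rule or multiplicity rule is given. Its size does rest on assumptions: 12 per arm, two-sided 5% t-tests, between-scale correlation 0.3-0.8 and no true effect on either scale. On those, accepting either scale at one visit carries a false-positive risk of about 8%-9.5%, against 0.5%-2% if both are required, and the plan does not say which applies. The sample-size statement belongs to no identifiable endpoint. The preliminary purpose lessens the consequence without removing it.

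**What to change.** Before the registration planned for the first month, name one primary scale at one visit and test it alone at two-sided 5%. For example: *Primary endpoint: change from baseline in upper-limb FM motor score at the end-of-intervention evaluation, real versus sham rTMS.* This is a default, not a finding that FM is the better measure. The primary aim speaks of functionality, and the sponsor may prefer ARA. Alternatively, keep FM and ARA at that visit as two primary endpoints, either sufficient, under Holm.

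Then:

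- Report the other scales and the one-month results as secondary, with 95% confidence intervals and no efficacy claim.
- State the effect size and SD behind the 95%/80% figure for the chosen endpoint.
- Make the reference to three tests agree with the scales named.

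**Cost.** Wording only, since the measures and visits are already planned. A positive result on a secondary scale or visit alone could no longer be claimed as efficacy. Holm keeps overall error at about 4%-5%. At a difference of 1.20 it lowers first-step power for a given scale from 80% to 70%, but the chance of at least one success is about 79%-88%, roughly equal to or above that of a single endpoint.
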